5.2 Patient Evaluation Flowsheet: Pre-Treatment, On-Study, and after Protocol Treatment
 For Patients Randomized to Durvalumab and Tremelimumab (Arm 2)

| Required Investigations | PRE-STUDY (≤14 days prior to randomization, unless otherwise indicated) | DURING Protocol Treatment Day 1 each cycle, and as clinically indicated (unless otherwise indicated) | AFTER Protocol Treatment is Permanently Discontinued ¹ | | | |
|---|--|---|---|--------------------------|---|---------------------------|
| | | | PRIOR to objective disease progression | | AFTER objective disease progression | |
| | | | 4 weeks after end of last cycle date | Every 4 weeks thereafter | 4 weeks after end of last cycle date ¹ | Every 12 weeks thereafter |
| History and Physical Exam² | | | | | | |
| Including: height (baseline only), weight, ECOG performance status, clinical tumour measurements (if applicable) | X | X | X | X | X | |
| Vital Signs (blood pressure, heart rate, temperature) | X | X ³ | | | | |
| Concomitant Medications | X | X | X | | X | |
| Overall Survival | | | | | | |
| Survival status assessment | | X | X | X | X | X ⁴ |
| Hematology^{2,5} | | | | | | |
| CBC, differential (including lymphocytes), platelets | X | X ² | X | X | X | X ⁵ |
| Coagulation^{2,5} | | | | | | |
| PTT, PT/INR | X | X ² | X | X | X | X ⁵ |
| Biochemistry^{2,5} | | | | | | |
| Serum Creatinine, Chloride, Sodium, Potassium, Calcium, Magnesium, Bilirubin, ALP, AST and ALT, LDH, Albumin, TSH ⁶ , Amylase, Lipase, Serum CEA | X | X ² | X | X | X | X ⁵ |
| Creatinine Clearance (calculated) | X | as clinically indicated | | | | |
| Glucose | X | as clinically indicated | | | | |
| Radiology⁷ | | | | | | |
| Chest/abdomen/pelvis CT or MRI scan | X ≤ 28 days | X ⁷ Every 8 weeks from randomization until objective disease progression (maintain schedule even if cycles are delayed) | | | | |
| Other scans as necessary to document all measurable and non-measurable disease | X ≤ 28 days | | | | | |
| Other Investigations | | | | | | |
| Pregnancy Test ⁸ | X | | | | | |
| ECG | X | as clinically indicated | | | | |
| Dipstick Urinalysis (including protein, specific gravity, glucose and blood) | X | | | | | |

table continued on next page ...

ADMIN UPDATE #1: 2018-JAN-24

| Required Investigations | PRE-STUDY (≤14 days prior to randomization, unless otherwise indicated) | DURING Protocol Treatment Day 1 each cycle, and as clinically indicated (unless otherwise indicated) | AFTER Protocol Treatment is Permanently Discontinued ¹ | | | |
|--|--|---|---|--------------------------|---|---------------------------|
| | | | PRIOR to objective disease progression | | AFTER objective disease progression | |
| | | | 4 weeks after end of last cycle date | Every 4 weeks thereafter | 4 weeks after end of last cycle date ¹ | Every 12 weeks thereafter |
| Correlative Studies | | | | | | |
| Archival Tissue Sample ⁹ (mandatory) | Availability of sufficient tissue must be confirmed prior to randomization | Submit tissue within 4 weeks of randomization | | | | |
| Whole blood, plasma and serum ⁹ (mandatory) | After randomization but before first dose of study treatment | To be done at 8 weeks and at the time of objective disease progression ¹⁰ , if not already done | | | | |
| Adverse Events | | | | | | |
| Adverse Event Assessment ¹¹ | X (To document residual adverse events from previous therapy and baseline symptoms) | X ¹² (To be evaluated continuously for adverse events) | X | X ¹³ | X ¹ | X ¹³ |
| Quality of Life | | | | | | |
| EORTC QLQ C30 ¹⁴ | X | At 4, 8, 12, 16 and 24 weeks after randomization, then every 12 weeks thereafter (until deterioration to ECOG PS 4 or hospitalization for end of life care) | | | | |
| 
 All patients will be seen at 4 weeks after the end of the last cycle date. Thereafter, continued follow-up is not required for patients who go off protocol treatment with unequivocal progressive disease, except to document ongoing toxicities (until resolved to < grade 2) and late toxicities (including second malignancies). For patients who go off protocol treatment with CR, PR, or SD ongoing, follow-up will be required every 12 weeks until relapse (see Appendix I for investigations to be performed). Death Report will be required for all patients. Due within 2 weeks of knowledge of death (see Appendix IV - Documentation for Study). Timing of Day 1 Assessments: Pre-treatment blood draws and physical exams may be done one working day prior to treatment if necessary, and when treatment is to begin on a Monday, may be done on the previous Friday (maximum 72 hours prior to treatment). In order to ensure that nadir counts are not missed, every effort should be made to do interim blood draws within 24 hours of the day specified in the protocol. If a patient shows an AST or ALT ≥ 3 x ULN together with total bilirubin ≥ 2 x ULN, refer to Appendix III for further instructions on cases of increases in liver biochemistry and evaluation of Hy's Law. These cases should be reported as SAEs if, after evaluation, they meet the criteria for a Hy's law case or if any of the individual liver test parameters fulfill any of the SAE criteria. Note: Labs do not need to be repeated Day 1, Cycle 1. In order to ensure that nadir counts are not missed, every effort should be made to do interim blood draws within 24 hours prior to the day specified in the protocol. Vital signs are to be monitored before, during, and after the infusion of tremelimumab and durvalumab with assessment of vital signs to be collected ≤ 30 minutes prior to start of infusion then every 30 ± 5 minutes during infusion and observation periods. A 1-hour observation period is recommended after the first infusion of tremelimumab, during which time durvalumab may be administered (see Section 7.1.3). A second 1-hour observation period is recommended after the first infusion of durvalumab. If no clinically significant infusion reactions are observed during or after the first cycle of tremelimumab and durvalumab, subsequent infusion observation periods can be at the Investigator's discretion but are recommended to be of 30 minutes, i.e., 30 minutes after tremelimumab infusion, during durvalumab infusion, and for 30 minutes after durvalumab infusion. For patients who receive only durvalumab, the recommended observation period is 30 minutes after infusion. In the event that patient is unable to attend clinic, post-progression follow-up may be by means of telephone contact. Hematology, Coagulation and Biochemistry investigation to be done after objective progression ONLY if there are ongoing hematologic AEs that are related to protocol treatment. If abnormal, T3 and T4 must be measured. To ensure comparability, scans must identify and report each lesion at baseline and at reassessment during treatment. These scans must be performed using identical technique (i.e. scans performed immediately following bolus contrast administration using a standard volume of contrast, the identical contrast agent, and preferably the same scanner). Tumour evaluations must be consistently performed every 8 weeks (i.e. at 8 weeks, 16 weeks, 24 weeks, 32 weeks etc. from randomization) until objective disease progression is documented (as described in Section 8). Sites should adhere to this calendar-based schedule regardless of any delays in treatment. If a radiology scan is done off schedule, future protocol-required scans should still be performed based on the original schedule, i.e. every 8 weeks counting from randomization (not from the date of the off schedule scan). For women of childbearing potential only. May be urine or serum. Pregnancy test (in women of childbearing potential), as part of Pre-Study Evaluation, may include an ultrasound to rule-out pregnancy. See Section 12.0 and the CO.26 Correlative Studies Laboratory Manual for details. Whole blood, plasma and serum should be obtained as close to the time of objective progression as possible and should be done within 28 days (e.g. at the next clinic visit). Blood for correlatives done within 28 days PRIOR to date of progression does not need to be repeated. Adverse Events to be evaluated using the NCI Common Terminology Criteria for Adverse Events (CTCAE v4.0) (see Appendix V). See Section 7 and Appendix III for additional monitoring of patients with toxicity. Follow every adverse event felt related to study therapy until resolved to ≤ grade 2 – i.e. follow-up every 12 weeks until deterioration to ECOG PS 4 and/or end of life care or until all toxicities thought to be possibly-, probably-, or definitely-related to durvalumab or tremelimumab have resolved, returned to baseline, or been deemed irreversible, whichever is longer. To be completed by patient in clinic. | | | | | | |

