1.3 Tertiary Objectives

- To determine the effect on quality of life (QoL) of the combination of durvalumab and tremelimumab and best supportive care *versus* best supportive care only in patients with refractory, advanced colorectal cancer.
- To determine the effect of tumour PD-L1 expression assessed by IHC on efficacy of the combination of durvalumab and tremelimumab and best supportive care *versus* best supportive care only in patients with refractory, advanced colorectal cancer.
- To explore association between putative biomarkers in archival tumour specimens and the potential for clinical benefit between the combination of durvalumab and tremelimumab and best supportive care *versus* best supportive care only in patients with refractory, advanced colorectal cancer.
- To explore association with baseline values and changes in putative biomarkers in blood, serum and plasma and the potential for clinical benefit between the combination of durvalumab and tremelimumab and best supportive care *versus* best supportive care only in patients with refractory, advanced colorectal cancer.

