- 4.2.8 Symptomatic or uncontrolled brain metastases requiring concurrent treatment, inclusive of but not limited to surgery, radiation and/or corticosteroids.
- 4.2.9 Receipt of live attenuated vaccination (examples include, but are not limited to, vaccines for measles, mumps, and rubella, live attenuated influenza vaccine (nasal), chicken pox vaccine, oral polio vaccine, rotavirus vaccine, yellow fever vaccine, BCG vaccine, typhoid vaccine and typhus vaccine) within 30 days prior to randomization.
- 4.2.10 Pregnant or lactating women.
- 4.2.11 Any active disease condition which would render the protocol treatment dangerous or impair the ability of the patient to receive protocol therapy.
- 4.2.12 Any condition (e.g. psychological, geographical, etc.) that does not permit compliance with the protocol.
- 4.2.13 Receipt of anti-cancer chemotherapy or biologic therapy within the lesser of i) 21 days, or ii) the usual cycle length of the regimen (e.g. 14 days for FOLFOX), prior to the first planned dose of durvalumab or tremelimumab. An exception is made for capecitabine and regorafenib, where a minimum of 10 days since last dose must be observed prior to the first planned dose of durvalumab or tremelimumab.
- 4.2.14 Receipt of radiotherapy or investigational agents within four weeks of first planned dose of durvalumab or tremelimumab, with the exception of a single dose of radiation up to 8 Gray (equal to 800 RAD) with palliative intent for pain control up to 14 days before randomization.
- 4.2.15 Any unresolved toxicity (CTCAE grade 2) from previous anti-cancer therapy. However, patients with irreversible toxicity that is not reasonably expected to be exacerbated by the investigational products in the Investigator's opinion may be included (e.g. hearing loss, peripheral neuropathy).

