5.1 Patient Evaluation Flowsheet: Pre-study (Baseline) and Post-randomization Follow-up
For Patients Randomized to Best Supportive Care (Arm 1)

| Required Investigations | PRE-STUDY (≤ 14 days prior to randomization, unless otherwise indicated) | PRIOR to objective disease progression (timing from randomization) | | AFTER objective disease progression (timing from randomization) |
|---|---|---|--|--|
| | | Every 4 weeks until objective disease progression | Every 8 weeks until objective disease progression (maintain schedule even if clinic visits are delayed) ³ | Every 12 weeks |
| History and Physical Exam | | | | |
| Including: height (baseline only), weight, ECOG performance status, clinical tumour measurements (if applicable) | X | X | | |
| Vital Signs (blood pressure, heart rate, temperature) | X | X | | |
| Concomitant Medications | X | X | | |
| Overall Survival | | | | |
| Survival Status Assessment | | X | X | X ¹ |
| Hematology | | | | |
| CBC, differential (including lymphocytes), platelets | X | X | | |
| Coagulation | | | | |
| PTT, PT/INR | X | X | | |
| Biochemistry | | | | |
| Serum Creatinine, Chloride, Sodium, Potassium, Calcium, Magnesium, Bilirubin, ALP, AST and ALT, LDH, Albumin, TSH ² , Amylase, Lipase, Serum CEA | X | X | | |
| Creatinine Clearance (calculated) | X | as clinically indicated | | |
| Glucose | X | as clinically indicated | | |
| Radiology³ | | | | |
| Chest/abdomen/pelvis CT or MRI scan ³ | X ≤ 28 days | | X ³ | |
| Other scans as necessary to document all measurable and non-measurable disease ³ | X ≤ 28 days | | | |
| Other Investigations | | | | |
| Pregnancy Test ⁴ | X | | | |
| ECG | X | as clinically indicated | | |
| Dipstick Urinalysis (including protein, specific gravity, glucose and blood) | X | | | |

table continued on next page ...

| Correlative Studies | | | |
|--|--|---|--|
| Archival Tissue Sample ⁵ (mandatory) | Availability of sufficient tissue must be confirmed prior to randomization | Submit tissue within 4 weeks of randomization | |
| Whole blood, plasma and serum ^{5,6} (mandatory) | X | To be done at 8 weeks, and at the time of objective disease progression ⁷ , if not already done | |
| Adverse Events | | | |
| Adverse Event Assessment ⁸ | X (To document residual adverse events from previous therapy and baseline symptoms) | X To be evaluated continuously for adverse events (until objective disease progression) | |
| Quality of Life | | | |

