7.0 TREATMENT PLAN

Although the Canadian Cancer Clinical Trials Group acts as the coordinating agency for the trial, the responsibility for the treatment of patients rests with each individual investigator.

In accordance with CCTG policy, protocol treatment is to begin within 2 working days of patient randomization.

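### The two flowsheets set different baseline windows by arm for the same mandatory biomarker blood, so baseline and change values can differ in timing between arms

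*Protocol*

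**What the plan says.** Protocol 5.1 (Arm 1) has a row for "Whole blood, plasma and serum", marked as mandatory, with a plain X in the column headed "PRE-STUDY (≤ 14 days prior to randomization, unless otherwise indicated". Nothing in the cell overrides that heading. Protocol 5.2 (Arm 2) has the same row under an equivalent heading, but the cell replaces the window with "After randomization but before first dose of study treatment". Protocol 7.0, like 4.1.19, says that "protocol treatment is to begin within 2 working days of patient randomization". Both arms have later draws at 8 weeks and at objective progression.

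The samples serve a tertiary objective in Protocol 1.3: "To explore association with baseline values and changes in putative biomarkers in blood, serum and plasma". Protocol 12.1 collects blood from all patients and names circulating tumour DNA as the priority assay.

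Exclusion 4.2.13 sets the washout from prior systemic therapy. It bars treatment "within the lesser of i) 21 days, or ii) the usual cycle length of the regimen (e.g. 14 days for FOLFOX"), counted back from the first planned dose. For capecitabine and regorafenib, "a minimum of 10 days since last dose must be observed prior to the first planned dose of durvalumab or tremelimumab".

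**The concern.** In the pre-study columns of the two flowsheets, this is the only row whose baseline timing depends on the arm. Laboratory tests, scans, ECG, tissue, adverse events and quality of life match. No reason is given for the exception.

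Two things follow. First, the site does not know the arm at screening. Drawing everyone then meets 5.1 but forces a second draw for Arm 2. Waiting for allocation meets 5.2 but puts BSC patients outside their window. Second, a baseline whose date is tied to allocation is a systematic difference between arms, and it does not average out as random variation in draw dates would. An earlier BSC baseline lengthens the interval to week 8 and can sit closer to prior therapy. Either could enter a between-arm comparison of baseline or change values without any effect of the study drugs.

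**Working it through.** The plan gives no figure for biomarker timing to reproduce. Its nearest design figure, 150 deaths (Protocol 13.3), does reproduce with the Schoenfeld formula: (1.645 + 0.842)² / [(1/3)(2/3)(ln 0.65)²] ≈ 150. It does not use the blood samples.

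**Draw windows (day 0 = randomization).**
- BSC: day -14 to 0 (5.1).
- Arm 2: day 0 up to the first dose (5.2). Two working days are 2 calendar days from Monday to Wednesday and 4 from Thursday or Friday, so the window is day 0 to +2, or +4 across a weekend.
- The windows meet only at randomization. The gap between a BSC and an Arm 2 draw runs from 0 to 14 + 2 = 16 days, or 14 + 4 = 18 across a weekend.

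**Baseline-to-week-8 interval.** Take week 8 as day 56 from randomization. This is an assumption for Arm 2, because the 5.2 cell names no starting point. Interval = 56 − draw day.
- BSC: 56 − 0 = 56 to 56 − (−14) = 70 days. The longest is 70/56 = 1.25 times the shortest.
- Arm 2: 56 − 4 = 52 to 56 − 0 = 56 days.
- If Arm 2 counted week 8 from a first dose on day +4, its interval would be 56 to 60 days. The arms would still differ.

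**Time since prior therapy at the draw.** Assume the shortest allowed washout w, applied before allocation to a planned first dose on day f. Last prior dose = f − w. Days since last dose = draw day − (f − w); a negative value means that the draw precedes the last dose.

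| f | w (days) | Last prior dose | BSC draw, day -14 | Arm 2 draw, day 0 |
|---|---|---|---|---|
| 0 | 21 | day -21 | 7 | 21 |
| 0 | 14 | day -14 | 0 | 14 |
| 0 | 10 | day -10 | -4 | 10 |
| +2 | 21 | day -19 | 5 | 19 |
| +2 | 14 | day -12 | -2 | 12 |
| +2 | 10 | day -8 | -6 | 8 |
| +4 | 21 | day -17 | 3 | 17 |
| +4 | 14 | day -10 | -4 | 10 |
| +4 | 10 | day -6 | -8 | 6 |

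Under the 21-day rule, even the earliest BSC draw follows the last dose. Under a 14-day cycle or the 10-day exception, an early BSC draw can fall on or before it. The closest Arm 2 draw is 6 days after. A BSC draw on day 0 has the same values as an Arm 2 draw on day 0.

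**Illustration only.** If a marker doubles every 4 to 8 weeks (assumed, not in the documents), a baseline drawn earlier by a given lead inflates the fold change by 2^(lead / doubling time). A 1-week lead gives 2^(1/8) = 1.09 to 2^(1/4) = 1.19. A 2-week lead gives 2^(2/8) = 1.19 to 2^(2/4) = 1.41. The documents do not say when sites actually draw, so the lead is assumed too.

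**The case against.** The strongest reply is that this is a wording inconsistency with little consequence. The BSC window runs up to randomization, so a site that draws on that day creates almost no difference. Draws on or before the last prior dose need an early draw, a near-minimum washout, and a short-cycle regimen, capecitabine or regorafenib. Eligibility also requires that standard regimens have failed or are unsuitable, and the documents do not show that a failed regimen still suppresses any marker. The objective is tertiary and exploratory, and the SAP contains no blood-biomarker analysis that could be biased. Collection details are left to a laboratory manual that is not available here and might harmonise the timing.

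Much of this stands, and it limits the point in three ways.
- A reader might infer that the BSC rule cannot be followed before the arm is known. It can: draw every patient before randomization. The cost is a second draw on Arm 2.
- A reader might infer that waiting for allocation leaves BSC patients with no baseline. A draw just after randomization is outside the literal window but may still be usable.
- A reader might infer that the bias must favour Arm 2. That needs a rising marker and earlier BSC draws, and any suppression by prior therapy is conjecture on these documents.

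The reply does not remove the conflict itself. The baseline rule in SAP 7.1 covers the Eligibility Checklist and Baseline Report, whereas Protocol Appendix IV puts correlative samples in a separate folder. The two-week limit there is for completing the form, not for drawing the blood.

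**Conclusion.** The concern holds in limited form. The flowsheets set arm-dependent baseline windows for one mandatory sample, and no available text reconciles them. Draw dates can differ between arms by 0 to 16 days, or 18 across a weekend. The intervals of 56 to 70 days on BSC and 52 to 56 on Arm 2 rest on counting week 8 from randomization. The difference in time since prior therapy rests on near-minimum washout and a planned first-dose date applied to both arms before allocation.

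The arms can differ; the documents do not show that they do, or by how much for any marker. The 9% to 41% inflation is an illustration and not an estimate. Only the tertiary blood-biomarker objective is affected.

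**What to change.** State one baseline window in both flowsheets, relative to randomization and feasible before allocation is known, for example on or close to the day of randomization, and delete the arm-specific text. Align the laboratory manual if it differs. The window should not also be required to follow the 4.2.13 washout: that washout runs to the planned first dose, which can fall after randomization, so a pre-randomization draw cannot always come after it. A common window does not abolish residual effects of prior therapy, but it stops them from depending on the arm by design.

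SAP 2.1 records that randomization closed on June 29, 2017, so new flowsheet wording cannot change this trial's baselines. For samples already drawn, the blood-biomarker analysis should:
- use the actual draw date when computing change;
- account for days since last prior therapy, because change per unit time alone does not remove carry-over;
- add a sensitivity analysis limited to baselines drawn close to randomization, for example within 2 working days, and report how many of the planned 60 BSC patients qualify, which is unknown now.

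The cost is an occasional tube wasted on a screen failure and a little more analysis work. The 180 patients and 150 deaths do not change.

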6.3 Randomization

Randomization will be provided electronically.

Note: The validity of results of the trial depends on the authenticity of and the follow-up of all patients entered into the trial. Under no circumstances, therefore, may an allocated patient's data be withdrawn prior to final analysis, unless the patient withdraws from the trial and requests that data collection/submission cease from the point in time of withdrawal.

All eligible patients admitted to the trial will be followed by the coordinating centre. It is the responsibility of the treating physician to satisfy himself or herself that the patient is indeed eligible before requesting registration/randomization.

All randomized patients are to be followed until death or until sites are informed by CCTG that further follow-up is no longer required. The follow-up requirements for ineligible patients are outlined in Section 4.2.

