10.0 PROTOCOL TREATMENT DISCONTINUATION AND THERAPY AFTER STOPPING

10.1 Criteria for Discontinuing Protocol Treatment

Patients may stop protocol treatment in the following instances:

- Intercurrent illness which would, in the judgement of the investigator, affect assessments of clinical status to a significant degree, and require discontinuation of protocol therapy.
- Unacceptable toxicity as defined in Section 7.0 and Appendix III.
- Tumour progression or disease recurrence as defined in Section 8.0.
- Request by the patient.

Efforts should be made to maintain the investigations schedule and continue follow-up, even if patients discontinue protocol treatment prematurely and/or no longer attend the participating institution.

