15.6 Centre Performance Monitoring

This study is eligible for inclusion in the Centre Performance Index (CPI).

Forms are to be submitted according to the schedule in the protocol. There are minimum standards for performance.

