APPENDIX IV - DOCUMENTATION FOR STUDY

Follow-up is required for patients from the time of randomization and will apply to all eligible patients.

This trial will use a web-based Electronic Data Capture (EDC) system for all data collection. For details of accessing the EDC system and completing the on-line Case Report Forms please refer to the “CCTG EDC Generic Data Management Guidebook” posted on the CO.26 area of the CCTG web-site (www.ctg.queensu.ca).

The electronic CRFs to be used in this trial, through the EDC system, are as follows:

| Electronic Folder | Timing | To be completed electronically | Supporting Documentation Required ¹ |
|---|--|--|--|
| Eligibility Checklist | | At the time of randomization | 
 • consent form² |
| Baseline Report | | Within 2 weeks of randomization | 
 • relevant pathology report(s) • RAS reports • relevant operative report(s) • relevant radiology reports (including CT/MRI abdomen/pelvis, CT/MRI chest, chest x-ray) • tumour measurement worksheet • ECG report |
| Correlative Studies Report (Tumour and Blood) | Continuous running-log folder See Section 5.0 | Information pertaining to tumour tissue submission must be completed as soon as possible after randomization, and tissue submitted within 4 weeks of randomization. | 
 • Consent form² • Diagnostic pathology report (for tumour tissue only) |
| | | Information pertaining to baseline/pretreatment blood collection for correlative studies (i.e. whole blood, plasma, serum) must be completed within 2 weeks of randomization. | |
| | | Information pertaining to post randomization blood collection samples (i.e. whole blood, plasma, serum) for correlative studies and banking should be completed within 2 weeks after collection of blood specimens. | |
| Concomitant Medication Report | Continuous running-log folder | | |
| Best Supportive Care Report (Arm 1 only) | Every 4 weeks (28 days) until objective progression | Within 2 weeks of the end of each reporting period | 
 • If available/applicable: • CT/MRI abdomen/pelvis report • CT/MRI chest • other radiology reports • tumour measurement worksheet • ECG report |

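### Arm 2 flowsheet footnote 1 waives follow-up after unequivocal progression, against the protocol's own 12-weekly survival checks, so overall survival could be informatively censored in one arm only

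*Protocol*

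**What the plan says.** Protocol 5.2, footnote 1, is attached to the heading over the Arm 2 post-treatment columns. It sets a visit 4 weeks after the end of the last cycle and then states that "continued follow-up is not required for patients who go off protocol treatment with unequivocal progressive disease, except to document ongoing toxicities" and late toxicities. It still asks for a Death Report on every patient, timed from when the site learns of the death.

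Other current text points the other way:

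- The row "Survival status assessment" in the same table is marked in the 12-weekly column after objective progression. Footnote 4 adds: "In the event that patient is unable to attend clinic, post-progression follow-up may be by means of telephone contact".
- Section 6.3: "All randomized patients are to be followed until death or until sites are informed by CCTG that further follow-up is no longer required".
- Appendix IV opens with "Follow-up is required for patients from the time of randomization and will apply to all eligible patients" and schedules a Short Follow-up Report every 12 weeks after progression, with no restriction to one arm.
- Section 10.1: "Efforts should be made to maintain the investigations schedule and continue follow-up, even if patients discontinue protocol treatment prematurely". Section 15.6: "Forms are to be submitted according to the schedule in the protocol. There are minimum standards for performance".
- Footnote 13 of the same table: "Follow every adverse event felt related to study therapy until resolved to" grade 2 or less, through 12-weekly follow-up.

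The Arm 1 flowsheet (5.1) has the same 12-weekly survival check and telephone allowance, but no waiver.

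SAP 7.6.1 censors living patients at the last date known alive. Its sources are the contact dates on the Best Supportive Care, 4-Week Post-Treatment, Follow-up, Short Follow-up and Minimal Follow-up Reports, or the last infusion date. The quality-of-life questionnaires, which continue after progression, are not listed.

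**The concern.** Overall survival is the primary endpoint. Where a site acts on the footnote, contact with an Arm 2 patient ends soon after progression, and that last contact becomes the censoring time. Progression carries information about survival, so the censoring is informative, and it arises in one arm only.

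The direction is not fixed. If the site still learns of every death, deaths count whenever they occur while living Arm 2 patients leave the risk set early, and the hazard ratio (HR) moves toward no benefit. If later deaths go unlearned, that bias shrinks and can turn in favour of Arm 2.

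The Short Follow-up Report is also the source for the SAP 7.8 table of anti-cancer treatment after progression, which could be incomplete in Arm 2.

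**Working it through.** **What the waiver removes.** In the Arm 2 column for 12-weekly contact after progression, the entries are survival status, laboratory tests (only for ongoing related adverse events) and adverse-event assessment. The footnote excepts toxicities. What it takes out of that column is therefore survival status.

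**Design figure reproduced.** Inputs (protocol 13.3 and 7.1.1): HR 0.65, two-sided alpha 10%, power 80%, 2:1 allocation. Schoenfeld: d = (1.645 + 0.842)² / [(2/3)(1/3)(ln 0.65)²] = 6.18 / (0.2222 × 0.1856) = 150, as stated. The BSC median of 4.5 months gives 4.5/0.65 = 6.9 months in Arm 2. The standard error of log HR at 150 deaths is √[1/(150 × 2/9)] = 0.173.

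**Event bound.** 180 − 150 = 30. If more than 30 Arm 2 patients (25% of 120) were dropped and their deaths never reported, 150 deaths could not be reached. Smaller losses would not stop the trigger.

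**Illustrative simulation, true HR 0.65.** From the documents: 180 patients, 2:1, BSC median 4.5 months, scans every 8 weeks, analysis at the 150th recorded death. Assumed: exponential survival; observed median PFS about 1.9 to 2.8 months; last contact 8 weeks after the progression scan; accrual over 18 or 10.6 months; the share of Arm 2 progressors affected; and three links between progression and survival (independent, correlated 0.6, or progression at a fraction of survival time). The test is an unstratified log-rank at two-sided 10%, whereas the SAP test is stratified. There are 1,500 to 3,000 runs per cell, and results are over runs reaching 150 deaths by 48 months.

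| Arm 2 progressors affected | Later deaths known | HR | Power |
|---|---|---|---|
| None | – | 0.65 | 80–82% |
| A quarter (about 21–24 patients) | all | 0.66–0.68 | 70–76% |
| A quarter | half | 0.63–0.67 | – |
| A quarter | none | 0.61–0.65 | – |
| Half | all | 0.67–0.73 | 57–74% |
| Any share, vital status updated to one cut-off | – | 0.64–0.65 | 80–82% |

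Hand check of the half-affected row: power ≈ Φ(|ln HR|/0.173 − 1.645). HR 0.73 gives Φ(0.17) = 57%, and HR 0.67 gives Φ(0.67) = 75%.

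The share of missed deaths at which the sign flips depends on the progression–survival link: about a quarter, about half, or nearly all. If every progressor were affected, 150 deaths would be reached by 48 months in 5 to 15% of runs with half the later deaths known and in none with no later deaths known, so no HR is quoted for those cases.

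**Wider assumptions at a quarter affected** (PFS setting 1.5, 2 or 3 months; last contact 0 to 16 weeks after the scan): HR 0.65–0.70 with all later deaths known, 0.62–0.68 with half, 0.59–0.66 with none. With a true HR of 1.0: 1.00–1.06, 0.96–1.04 and 0.91–1.01.

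**Second model** (illness–death, exponential survival, share counted among all Arm 2 patients, all deaths known): power falls from 79% to 68% with a quarter affected and 56% with half.

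**Would it be seen?** With a quarter affected, 150 deaths are still reached by 48 months in 99 to 100% of runs even if no later deaths are known. Median follow-up in SAP Table 2 is only 0 to 2 months shorter in Arm 2. The mean gap from last contact to cut-off, among patients not known dead, separates the arms better: 2.2–3.4 months in Arm 2 with all deaths known, or 5.3–6.7 with half known, against 1.2–1.4 in Arm 1.

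**The case against.** The strongest reply is that the rest of the protocol already requires survival follow-up. A site applying the waiver would breach Section 6.3 and miss a scheduled form, and Section 5.3 wants the date of death even for ineligible patients. Nothing in the documents shows that any site applied it. The footnote can also be read as ending clinic visits rather than vital-status contact, since it speaks of patients being seen and keeps the Death Report. These points limit how often the problem is likely to occur. They do not remove it: the documents give no rule of precedence between a footnote and its table, and the Death Report depends on hearing of the death.

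The magnitude is assumption-driven, and that stands. At a quarter affected the HR range straddles 0.65. With all deaths known, the shift is ln(0.66/0.65)/0.173 = 0.09 to ln(0.68/0.65)/0.173 = 0.26 standard errors. The illness–death model with a true HR of 1.0, a quarter affected and later deaths unlearned gives HR 0.98–1.00 and a favourable tail of 5.5–7.0%, against 5.3–6.3% with no waiver. No direction should be claimed.

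Three smaller points also stand. The quality-of-life schedule is 4, 8, 12, 16 and 24 weeks before it becomes 12-weekly. Protocol 13.2 censors at the last date known alive without listing sources, so the gap in the SAP list matters only if that list is read as exhaustive. SAP 7.6.5 already mentions a final clinical cut-off, but for response, with no vital-status rule.

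**Conclusion.** The concern holds. The footnote contradicts its own table, Section 6.3 and Appendix IV, and it does so in Arm 2 only. With the SAP censoring rule, following it would make overall-survival censoring depend on progression in one arm. This should be fixed before the survival analysis.

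The size is conditional. With a quarter of Arm 2 progressors affected, the HR moves from 0.65 to somewhere between 0.61 and 0.68 depending on how many later deaths are learned, and power falls to 70–76% if all of them are. With half affected and all deaths known, power is 57–74%. These figures rest on the assumed PFS, last-contact time, progression–survival link and affected share. Confidence is medium because the documents cannot show whether any site used the waiver. Large losses would reveal themselves by stalling the 150-death trigger; modest ones would be hard to detect.

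**What to change.** Randomization closed on 29 June 2017 (SAP 2.1), so the working remedy is in the analysis plan.

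1. Add to SAP 7.6.1 a single overall-survival data cut-off tied to the 150th recorded death, with vital status updated to that date for every patient not known dead, by the same rule in both arms. SAP Section 5 calls for at least 150 recorded deaths, so further deaths found in the update are simply included.
2. Report, by arm, the time from last date known alive to cut-off.
3. Reword 5.2 footnote 1 so that any waiver covers clinic investigations only, and survival status continues every 12 weeks in both arms (telephone allowed) until death or notice from CCTG.

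The simulated recovery to full power assumes that the vital-status update is complete.

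Separately, and without bearing on the conclusion, four items in the footnote need reconciling with the table and appendices:

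- the follow-up interval for patients off treatment in CR, PR or SD (12-weekly versus 4-weekly);
- the pointer to Appendix I, which holds the performance-status scales;
- the post-treatment visit (4 weeks after the end of the last cycle versus after the last infusion);
- the Death Report deadline (2 weeks from knowledge versus 4 weeks from death).

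Cost: one SAP sentence, one vital-status query for about 180 − 150 = 30 patients (about 24 of them in Arm 2 under the design assumptions), one by-arm summary, one footnote rewording and four small corrections. The sample size and event target do not change.
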